### **3.2 Study population, exposures, outcomes and covariates**

#### **3.2.1 Study populations/subgroups**

##### *Study population for main analysis (primary objective and secondary objective #1)*

- Pregnant women received prenatal care at KPSC
- Exposed cohort: vaccinated with Boostrix on the 1st day of the 27th week of pregnancy or later during the pregnancy and were not vaccinated with any other Tdap vaccine at any other time during the pregnancy or
- Unexposed cohort: pregnant at least one day during the approximate estimated period between 1/1/2012-12/31/2013 and did not receive any Tdap vaccine during the pregnancy
- Continuous membership (allowing up to a 31-day gap) between the 1st day of the 27th week of pregnancy and the index (vaccination) date

The unexposed cohort will be 1:1 matched to the exposed cohort on age at pregnancy start ( $\pm 1$  year), race/ethnicity (White, Black, Hispanic, Asian, and Other), and multiple gestation (yes/no). Every unexposed woman will be assigned an index date that is determined by the number of days from pregnancy start to the Boostrix vaccination date of her matched exposed woman. The same number of days calculated in the exposed woman will be added to the pregnancy start of the unexposed woman to determine her index date.

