3. STUDY DESIGN

3.1. Study setting

KPSC is an integrated healthcare system that provides comprehensive prepaid health services for its 4.4 million members. There are 15 medical centers that include a total of 225 medical office buildings throughout Southern California. Members are racially diverse and include the entire socio-demographic spectrum, and over 99% are community-dwelling. The demographic makeup of the KPSC membership closely mirrors the Southern California population and the California census population (20). Compared to the racial/ethnic distribution of the U.S. population, the KPSC membership has twice as many individuals of Asian descent and three times as many Hispanics. Data regarding demographics, services, diagnoses, and procedures are tracked in the KPSC EHR (Health Connect) from the outpatient, emergency department, and hospital settings. Health Connect is the legal record of all medical care received within the KPSC system. Records of vaccinations and medical events can only be entered by medical staff. Pharmacy records and vaccinations are linked through patients' unique medical record numbers (MRNs). Vaccinations received outside of the health plan are recorded with appropriate documentation.

KPSC is a pre-paid health care system. Vaccines are typically provided to KPSC members at no charge, which is an incentive for members to receive immunizations within the system. Also, there is a very strong motivation for members to use services internally. For outside providers to be reimbursed by the health plan for covered emergent or contract care, claims must be submitted with documentation of the episode of care. Thus, the capture of care delivered to members by electronic administrative data is reasonably assumed to be very comprehensive. The KPSC Regional Immunization Practice Committee (RIPC) makes recommendations to ensure appropriate use of vaccination and implementation of new ACIP immunization recommendations within KPSC.

Standard of care regarding use of Tdap in pregnant women

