3.2. Feasibility assessment

The following tables display data to describe Tdap vaccination among pregnant women at seven selected KPSC medical centers that will administer the Boostrix vaccine.

Approximately 15,000 women vaccinated with Boostrix will be included in this study, over approximately a one-year period.

Pregnant women receiving the Tdap vaccine

The following table provides demographic information on pregnant women receiving the Tdap vaccine at seven selected medical centers at KPSC ([Table 1](#)). There were 19,804 pregnant women receiving the vaccine within these medical centers in 2016. Over half of them were of Hispanic race/ethnicity (57%). The age distribution shows that pregnant women aged 27-35 years old made up more than half (55%) of the Tdap-exposed pregnant women ([Table 2](#)).

Table 1 Race/ethnicity of women receiving the Tdap vaccine during pregnancy at seven selected medical centers at Kaiser Permanente Southern California, 2016

Mother's race/ethnicity	Frequency	Percent
Asian	2,494	12.6%
Black	1,643	8.3%
Hispanic	11,354	57.3%
Multiple	512	2.6%
Native American/ Alaskan	11	0.1%
Others	24	0.1%
Pacific Islander	23	0.1%
Unknown	33	0.2%
White (Non-Hispanic white)	3,710	18.7%
TOTAL	19,804	100%

Table 2 Age of women at Tdap vaccination during pregnancy at seven selected medical centers at Kaiser Permanente Southern California, 2016

Mother's age at vaccination (years)	Frequency	Percent
15-26	5,785	29.2%
27-35	10,858	54.8%
36-45	3,132	15.8%
>45	29	0.2%
TOTAL	19,804	100%

Membership among Tdap vaccinated pregnant women

At seven selected medical centers within KPSC, 18,875 (95.3%) pregnant women had continuous membership (allowing up to a 31-day gap) at least from the start of the 27th week of pregnancy (Table 3). There were 16,147 (82%) women who were members since the beginning of pregnancy.

Table 3 Membership among women receiving the Tdap vaccine during pregnancy at seven selected medical centers at Kaiser Permanente Southern California, 2016

Membership during pregnancy*	Frequency	Percent
Gestation: 0 to 26 weeks only	260	1.3%
Gestation: 27 weeks to delivery only	2,728	13.8%
Gestation: 0 weeks to delivery	16,147	81.5%
Partial membership**	669	3.4%
TOTAL	19,804	100%

* Represents women with membership (allowing up to a 31-day gap) during the entire indicated period.

** 447 had membership during the post-vaccine pregnancy period

Gestational age at Tdap vaccination

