4. STUDY POPULATION/CASE DEFINITION(S)

4.1. Study population

The exposed and unexposed cohorts will consist of pregnant women with evidence of prenatal care and continuous membership (allowing up to a 31-day gap) at KPSC between the 1st day of the 27th week of gestation and the index (vaccination) date.

Women will be considered exposed if they received Boostrix on or after the 1st day of the 27th week of gestation at selected ob-gyn clinics at seven medical centers throughout KPSC (vaccination period planned to begin in January 2018). Unexposed pregnant women comprise women pregnant sometime during the approximate estimated period between 1/1/2012 and 12/31/2013 who did not receive any Tdap vaccine during pregnancy. If needed, we will consider adding additional years to increase the eligible number of unexposed pregnant women. Gestational age will be estimated from the most reliable estimated date of delivery (EDD) which is based on the last menstrual period, the first accurate ultrasound examination, or both. Obstetric providers are recommended to reference guidelines from the American College of Obstetrics and Gynecology (ACOG) to calculate EDD (21). Pregnancy start date will correspond to a gestational age of 0 weeks.

Matching process for pregnant women who were vaccinated with Boostrix after the 27th week of gestation

The unexposed cohort will be matched 1:1 to the exposed group for comparisons of maternal and infant adverse events between the two cohorts. Every unexposed woman will be assigned an index date that is determined by the number of days from pregnancy start to the Boostrix vaccination date of her matched exposed woman. The same number of days calculated in the exposed woman will be added to the pregnancy start of the unexposed woman to identify her index date.

Existing health conditions, age, lifestyle factors, and conditions of pregnancy can place a pregnancy at risk (22). Therefore, matching variables include maternal age at pregnancy start (\pm 1 year), race/ethnicity (White, Black, Hispanic, Asian, and Other) and multiple gestation. Other pregnancy high-risk conditions will be considered as potential covariates in the analysis (see Section 6.2.1 Covariates).

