### **3. STUDY DESIGN**

#### **3.1 Overview of study design**

This is an observational retrospective matched cohort study. The study will be conducted among pregnant women who are members of KPSC.

The exposed cohort (from the 27th week of gestation) will consist of pregnant women who received the Tdap vaccine (Boostrix) on or after the 1st day of the 27th week of pregnancy during the vaccination period at ob-gyn clinics of seven selected medical centers. Approximately 15,000 women vaccinated with Boostrix will be included in this study over approximately a one-year period from January 2018 to January 2019.

The unexposed cohort will consist of women, pregnant sometime during the approximate estimated period from 1/1/2012 to 12/31/2013 who never received Tdap vaccine during pregnancy. The unexposed cohort of pregnant women will be matched 1:1 to the exposed cohort of pregnant women for comparisons of maternal and infant AEs between the two cohorts.

Subject-level data will be collected for pregnant women and their infants through the EHR. For each individual pregnant woman, analytical follow up will begin on the date they receive the Boostrix vaccine, or the index date for the unvaccinated cohort, and will end on the date of

disenrollment or the end of pregnancy, whichever came first. For the maternal death endpoint, pregnant women will be followed for 42 days after the end of pregnancy. Infants born in KPSC hospitals will be followed for 6 months.

In addition, women vaccinated with Boostrix before the 27th week of gestation, with membership at the date of vaccination, and who were not vaccinated with any other Tdap vaccine at any other time during the pregnancy will be included for a descriptive analysis (single arm).

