### 3.2.4 Covariates

Covariates (Table 2) to be collected and explored include medical conditions indicative of a high-risk pregnancy and other relevant baseline characteristics. The algorithms for identification of high-risk medical conditions are described in the DMP.

Table 2. List of covariates (all covariates will be treated as categorical in the analyses)

High-risk medical condition
Thyroiditis (present/absent)
Diabetes (present/absent)
Other autoimmune diseases (present/absent)
Renal diseases(present/absent)
Cardiac diseases (present/absent)
Pre-pregnancy obesity (BMI>40: yes/no/missing)
Pre-existing hypertension (present/absent)
Rhesus sensitization (present/absent)
HIV infection (present/absent)
Syphilis infection (present/absent)
Cervical incompetence (present/absent)
Lifestyle factors
Smoking status from pregnancy start to index date (Yes/No)
Alcohol use from pregnancy start to index date (Yes/No)

Enrollment
Length of membership prior to 27 weeks gestation (but after pregnancy start) – having continuous membership from pregnancy start to index date (Yes/No)
Medicaid insurance (public health insurance: Indicator of low-income status) – any Medicaid enrollment from pregnancy start to index date (Yes/No)
Utilization
Health care utilization (receipt of medical care) from pregnancy start to index date
Any hospitalization or ED visit (Yes/No)
Number of outpatient visits (0-4/5-12/ $\geq 13$ )
Maternal Data
Number of previous pregnancies (0/1/ $\geq 2$ /Missing)
History of pregnancy loss (Yes/No)
Season of pregnancy start (September-March/April-August)
Vaccine
Receipt of other vaccines during pregnancy, e.g., influenza vaccine (Yes/No)
Receipt of vaccines containing diphtheria, tetanus toxoid or pertussis antigens within one year before pregnancy (Yes/No)
Matching variables
Race/Ethnicity (White/Black/Hispanic/Asian/Other)
Multiple gestation (Yes/No)
Age at pregnancy start (years)

Smoking status will be defined as current smoker or not. If patients reported they smoked any time from pregnancy start to index date, then they will be current smokers. Alcohol use will be defined in a similar fashion.

Length of membership prior to 27 weeks gestation (but after pregnancy start) will be defined as a dichotomous variable of having continuous membership (allowing up to a 31-day gap) from pregnancy start to index date.

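### Exposed women come from seven of KPSC's 15 medical centers, but nothing in the protocol or SAP limits the unexposed women to those centers, and center is not matched on, adjusted for or tabulated

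*SAP*

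**What the plan says.** Protocol 3.1 describes the system: "There are 15 medical centers that include a total of 225 medical office buildings". Protocol 4.1 takes exposed women "at selected ob-gyn clinics at seven medical centers throughout KPSC", and SAP 3.1 likewise takes them "during the vaccination period at ob-gyn clinics of seven selected medical centers".

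The same part of protocol 4.1 defines the comparators by period and vaccination status only: "Unexposed pregnant women comprise women pregnant sometime during the approximate estimated period between 1/1/2012 and 12/31/2013 who did not receive any Tdap vaccine during pregnancy". SAP 3.2.1 does the same: "Unexposed cohort: pregnant at least one day during the approximate estimated period between 1/1/2012-12/31/2013 and did not receive any Tdap vaccine during the pregnancy". Both cohorts also need KPSC prenatal care and membership. The inclusion criteria in protocol 4.4 add no center limit.

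On control of differences between the cohorts:

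- **Matching.** In protocol 4.1, "matching variables include maternal age at pregnancy start" (within one year), race/ethnicity and multiple gestation. SAP 3.2.1 has the same three.
- **Covariates.** SAP 3.2.4 says: "Covariates (Table 2) to be collected and explored include medical conditions indicative of a high-risk pregnancy and other relevant baseline characteristics". Neither SAP Table 2 nor the list in protocol 6.2.1 contains center.
- **Baseline table.** SAP Table Shell 2 has no center row.
- **Limitations.** Protocol 7 and SAP 5.4 discuss calendar time, coding and confounding by indication, but not site.

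**The concern.** A historical comparator carries calendar-time differences that cannot be designed away, and the plan says so. Site differences are another matter: they depend on which pool the comparators are drawn from, and that is the study team's choice. If the wider pool is used, any difference in case mix or obstetric practice between the seven centers and the other eight that survives matching and adjustment enters the relative risk. The covariate screening in SAP 3.2.4 works from a list without center, and the baseline table would not show an imbalance.

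The two directions have different consequences. Lower rates at the other centers push the relative risk up, which uses part of the 1.25 design-bias allowance in SAP 3.3 and can produce false signals on secondary endpoints. Higher rates push it down. That makes non-inferiority easier to declare and starts no investigation, because SAP 4.5 acts only when a two-fold risk is not ruled out or a secondary risk is elevated.

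**Working it through.** **1. The plan's own power.** Inputs from SAP 3.3: 15,000 per cohort, 1% unexposed rate, true RR 1.25, margin 2, one-sided alpha 0.025/4 = 0.00625. The Miettinen-Nurminen calculation gives 95.7%, the stated figure. A Wald calculation on log RR gives 96.5%. The stated power is not in error.

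**2. Share of comparators from other centers (q).** Protocol 3.2 reports: "There were 19,804 pregnant women receiving the vaccine within these medical centers in 2016". Table 5 gives 38,475 for KPSC in 2016.

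- By vaccinated women: q = 1 − 19,804/38,475 = 0.485, or about 7,280 of 15,000.
- By center count: q = 8/15 = 0.533, or 8,000 of 15,000.

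Both are proxies for unvaccinated women in 2012-2013.

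**3. Effect on the relative risk.** Let x be the residual rate at other centers relative to the seven, after matching and adjustment. The RR is multiplied by 1/[(1 − q) + q·x]. No document gives x, so the values below are assumptions.

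| x | q = 0.485 | q = 0.533 |
|---|---|---|
| 0.8 | 1.11 | 1.12 |
| 0.9 | 1.05 | 1.06 |
| 1.11 | 0.95 | 0.94 |
| 1.25 | 0.89 | 0.88 |

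For site alone to multiply the RR by 1.25, x = 1 − 0.2/q = 0.59 to 0.63. For a factor of 0.8, x = 1 + 0.25/q = 1.47 to 1.52.

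**4. Primary endpoints.** With factors of 1.12 and 0.88, an observed bound of 2 corresponds to a true bound of 2/1.12 = 1.79 and 2/0.88 = 2.27. If site bias is added on top of RR 1.25, Miettinen-Nurminen power is:

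- seven-center rate 1%: 88-89% at x = 0.9 and 74-77% at x = 0.8;
- seven-center rate 2%: above 99% at x = 0.9 and 97-98% at x = 0.8.

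**5. Secondary endpoints.** SAP 4.3 flags a risk when the lower 95% limit exceeds 1. Wald calculation, 15,000 per cohort, q = 0.485, no true effect. Example at a seven-center rate of 1% and x = 0.8: the pool rate is 0.01 × 0.903 = 0.00903, log(0.01/0.00903) = 0.102, SE = √(0.99/150 + 0.991/135.4) = 0.118, and 1 − Φ(1.96 − 0.102/0.118) = 14%.

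| Seven-center rate | No site bias | x = 0.9 | x = 0.8 |
|---|---|---|---|
| 1% | 2.5% | 6% | 14% |
| 2% | 2.5% | 9% | 23% |

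In the other direction, power to flag a true RR of 1.25 at a 2% rate falls from 83% to 62% at x = 1.11 and to 31% at x = 1.25.

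**6. Can the seven centers supply the comparators?** Table 5 gives 34,486 + 29,519 = 64,005 pregnancies without Tdap in 2012-2013. The seven-center share is 64,005 × 0.515 = 32,945, or × 7/15 = 29,869. Applying the 95.3% membership in protocol 3.2 leaves 31,396 or 28,465. Divided by 15,000, that is 2.1 or 1.9 per exposed woman before matching losses. Table 5 does not say whether pregnancies ending before week 27 are counted. If 20% were unusable (assumption), 1.5 to 1.7 remain.

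**7. Precision of a restricted sensitivity analysis.** Keeping only seven-center comparators from an unrestricted match leaves 15,000 × 0.515 = 7,721, or × 7/15 = 7,000. Wald power at RR 1.25 is then 84% or 81% at a 1% rate, and about 99% at 2%.

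**The case against.** The strongest reply is that the plan never says comparators come from all 15 centers. That reading rests on the absence of a limit. The Data Management Plan was not available and Figure 1 is not shown, so either may hold the restriction. This stands as a caveat. If the pool is already restricted, the remedy is one sentence in each document.

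Second, no site effect is shown. KPSC has one health record and its providers generally follow common guidelines, two primary endpoints are chart confirmed, SGA uses a fixed reference, and the primary models force in diabetes, pre-existing hypertension (except for preeclampsia), Medicaid and utilization. These may remove much of any difference. They do not equalize obstetric practice, and without a center row nobody could check. The protocol's wording on covariates leaves room to add center, but nothing requires it.

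Third, a reader might infer that the primary non-inferiority conclusions are in doubt. The documents do not support that. The margin was set partly with possible bias in mind (SAP 5.3), power already allows 1.25, and site alone would need residual rates 38-41% lower or 47-52% higher to reach that factor. The plan also assigns robust variance to all four primary endpoints and reserves it for incidence above 2%, which suggests that all four are expected above the 1% used for power.

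Fourth, a late change is not free. Exposure ran from January 2018 to January 2019, and the Amendment 2 rationale already compares missing blood-loss data between the cohorts, so comparator data may have been examined. Redrawing the pool could mean rematching, renewed unmasked chart abstraction and a comparator changed after data were seen. This stands and shapes the fix.

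**Conclusion.** The point holds as a cheap improvement to the comparability of the cohorts, not as a flaw that invalidates the design. As written, roughly half the comparators (48.5-53.3% by proxy) could come from centers with no exposed women, and no listed step would detect or correct the difference. For assumed residual rate ratios of 0.8 to 1.25 the RR factor runs from about 1.12 to 0.88; its true size and direction cannot be known from the documents. A primary conclusion is unlikely to change. The main exposure is the secondary endpoints, where a factor of this size could raise a false signal or mask a true one.

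This rests on three assumptions: silence means no restriction, 2016 vaccinated women or center counts approximate the distribution of unvaccinated women in 2012-2013, and some center difference remains after matching and adjustment.

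**What to change.** 1. In protocol 4.1 and 4.4 and SAP 3.2.1, state that unexposed women are drawn from the same seven centers, assigned by center of prenatal care before the index date. Leave the three matching variables unchanged.
2. Add center to SAP Table Shell 2 in any case.
3. If matching or chart review is already complete, or too few matches result, keep the matched cohort. Pre-specify a sensitivity analysis of all primary and secondary endpoints restricted to seven-center comparators. This breaks pairs, so include the matching variables in those models, as SAP 4.2 already does for SGA and preterm delivery.

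**Cost.** A center must be assigned to historical pregnancies, and some sparse strata may go unmatched. Redrawing the pool late may require rematching and re-abstraction. The sensitivity analysis is less precise (81-84% power at a 1% rate, about 99% at 2%). With about 1.9 to 2.1 potential comparators per exposed woman before matching losses, early restriction should in principle keep 15,000 per cohort and the planned power. Restriction removes only center differences that are stable over time; changes within the seven centers between 2012-2013 and 2018 remain part of the historical comparison.

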There were 19,554 (98.7%) pregnant women who received Tdap vaccination at or after 27 weeks of pregnancy (Table 4). There were 18,611 (94.0%) women who were vaccinated between 27 and 36 weeks gestation.

Table 4 Gestational age of women at Tdap vaccination during pregnancy at seven selected medical centers at Kaiser Permanente Southern California, 2016

Gestational age at vaccination	Frequency	Percent
<27 weeks	250	1.3%
27 weeks to 32 weeks	15,111	76.3%
33 weeks to 36 weeks	3,500	17.7%
>36 weeks	943	4.8%
TOTAL	19,804	100%

Note: Only those women meeting eligibility criteria, including membership, will be included in the analysis.

Rationale for historical comparison cohort

The estimated period of 1/1/2012-12/31/2013 was chosen for the unvaccinated comparison group because Tdap uptake ranged between 27% and 38% during this time (Table 5). The aim is to restrict the unvaccinated population to approximately 2012-2013 to minimize the concerns of confounding by indication. Given that Tdap uptake exceeded 65% starting in 2014, a concurrent unvaccinated cohort will yield a small and selective sample, and is not representative of an unvaccinated group.

Table 5 Tdap vaccine receipt during pregnancy at Kaiser Permanente Southern California, 2011-2016

Year	Tdap during pregnancy		No Tdap during pregnancy	
	Frequency	Percent	Frequency	Percent
2011	18325	40.0%	27471	60.0%
2012	13128	27.6%	34486	72.4%
2013	18309	38.3%	29519	61.7%
2014	32660	65.3%	17366	34.7%
2015	35754	68.4%	16513	31.6%
2016	38475	69.3%	17058	30.7%

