4.4. Inclusion criteria

- Pregnant women with prenatal care and continuous membership (allowing up to a 31-day gap) at KPSC between the 1st day of the 27th week of gestation and the index (vaccination) date.
- **Exposed cohort** (from the 27th week of gestation): Pregnant women vaccinated with Boostrix on or after the 1st day of the 27th week of gestation; who were not vaccinated with any other Tdap vaccine at any other time during the pregnancy in scope of this study.
- **Unexposed cohort:** Women matched to the exposed cohort and pregnant sometime during the approximate estimated period between 1/1/2012-12/31/2013 and did not receive any Tdap vaccine during the pregnancy in scope of this study.

For the analysis of congenital anomalies among live births, at birth and through six months of age, the following additional inclusion criteria for infants will be applied:

- Live born
- Born in KPSC hospitals

Note: Pregnant women vaccinated with Boostrix during pregnancy before the 27th week of gestation, with membership at the date of vaccination, and who were not vaccinated with any other Tdap vaccine at any other time during the pregnancy in scope of this study will be part of a descriptive analysis (secondary objective).

5. DATA COLLECTION AND MANAGEMENT (amended 12 November 2019)

[figure not shown]
Vaccination and medical event data will be extracted directly from the EHR (Health Connect), which is the legal record of all medical care received within the KPSC system. [Figure 1](#) provides an overview of the data flow for this study. All details of a patient encounter, including diagnoses, procedures, and physician's notes, are entered into the EHR at the point of care. All vaccinations are entered into the EHR when they are given, with vaccine, dose, manufacturer, and lot number entered at the time of vaccination. Vaccinations received outside of the health plan are recorded with appropriate documentation. Records of vaccinations and medical events can only be entered by medical staff. Endpoints of interest will be extracted from the EHR using the pregnancy episode flowsheet, diagnosis codes (ICD-9 and ICD-10 codes), procedure codes, or death records.

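### Comparators are admitted by any pregnant day in 2012-2013 and not by index date, so an estimated 12-22% would be indexed in 2014 and 4.5-10% in 2011, the latter only if still pregnant on 1/1/2012

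*SAP*

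**What the plan says.** - **Admission.** SAP 3.2.1 requires an unexposed woman to have been "pregnant at least one day during the approximate estimated period between 1/1/2012-12/31/2013 and did not receive any Tdap vaccine during the pregnancy". Protocol 4.4 words it as "pregnant sometime during the approximate estimated period between 1/1/2012-12/31/2013", and protocol 4.1 agrees.
- **Index date.** SAP 3.2.1, on how this date is set: "The same number of days calculated in the exposed woman will be added to the pregnancy start of the unexposed woman to determine her index". Since the matched exposed woman was vaccinated in week 27 or later, the comparator's index date falls at that same late gestational age.
- **Follow-up.** SAP 3.1: "analytical follow up will begin on the date they receive the Boostrix vaccine, or the index date for the unvaccinated cohort".
- **Matching and covariates.** Matching is on age, race/ethnicity and multiple gestation. SAP Table 2 lists season of pregnancy start but not calendar year.
- **Why 2012-2013.** Protocol 3.2 chose these years because uptake was 27-38%, to limit confounding by indication. It adds: "Given that Tdap uptake exceeded 65% starting in 2014, a concurrent unvaccinated cohort will yield a small and selective sample".
- **Extension.** Protocol 4.1: "If needed, we will consider adding additional years to increase the eligible number of unexposed pregnant women". No direction or limit is given.

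**The concern.** Eligibility is judged on one date and follow-up starts on another, which causes a problem at each edge of the window.

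**Right edge.** A woman who conceives late in 2013 is eligible although her index date and all her follow-up fall in 2014. By then Tdap in every pregnancy had been the health plan's recommendation for over a year (protocol 3.1, December 2012). Women still unvaccinated could differ systematically from those of 2012-2013, which is the worry that led the protocol to choose the earlier window.

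**Left edge.** A woman indexed late in 2011 enters only if her pregnancy lasted to 1/1/2012. An otherwise identical woman who delivered preterm in December 2011 is left out. The exposed cohort is entered at vaccination and meets no such condition. The comparator alone therefore loses some preterm deliveries and other pregnancy-ending events.

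The report would not reveal either problem: no table shell shows index year and no sensitivity analysis by index year is planned. Signal investigation (SAP 4.5) starts only after an adverse result, so a bias toward a lower relative risk would trigger nothing.

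**Working it through.** **1. The plan's own figure.** The plan states 95.7% power for 15,000 women per cohort, comparator incidence 1%, true RR 1.25, margin 2 and one-sided 0.625%. Score test with rates constrained to p1 = 2·p0:
- Constrained rates: 0.00749 and 0.01499.
- Null SE = √[(0.01499×0.98501 + 4×0.00749×0.99251)/15,000] = 0.001723.
- Alternative SE = √[(0.0125×0.9875 + 4×0.01×0.99)/15,000] = 0.001861.
- Power = Φ[(0.0200 − 0.0125 − 2.498×0.001723)/0.001861] = Φ(1.72) = 95.7%.

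The figure is reproduced. It depends only on sample size, incidence, RR and alpha, so the admission rule does not alter it.

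**2. Dates.** Taking 27 weeks as 189 days, a pregnancy starting 26 June 2013 reaches that point on 1 January 2014. With the protocol's example index day of 194, a start on 31 December 2013 gives an index date of 13 July 2014.

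**3. Share of comparators by index year.** Inputs:
- Protocol Table 4: index gestational age, 15,111 / 3,500 / 943 women at 27-32 / 33-36 / >36 weeks.
- Protocol Table 5: unvaccinated pregnancies, 27,471 / 34,486 / 29,519 / 17,366 in 2011-2014.
- Assumed, not in the documents: uniform pregnancy starts, mean length 273 days (range 266-280), SD 12, and matches drawn evenly from the eligible pool.

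Under these inputs the mean index day is 217.6 and mean follow-up is 55.8 days. Hand check with Table 5's year read as index year:
- 2014: 217.6 × 17,366/365 = 10,353
- 2013: 29,519
- 2012: 34,486
- 2011: 55.8 × 27,471/365 = 4,200
- Total 78,558, so 2014 = 13.2% and 2011 = 5.3%.

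Simulated pregnancies give nearly the same, and show how much the reading of Table 5 matters:

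| Reading of Table 5 year | Indexed 2014 | Indexed 2011 |
|---|---|---|
| Index year | 13.2% | 5.4% |
| Delivery year | 13.4% | 6.8% |
| Pregnancy-start year | 20.8% | 5.0% |
| Unweighted | 21.7% | 5.6% |

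Varying pregnancy length and fixing the index day at 194, 203 or 210 widens the ranges to about 12-22% and 4.5-10%. In 15,000 comparators that is 1,800-3,300 and 675-1,500 women.

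**4. Left-edge effect on preterm delivery.** Women indexed in 2011 carry on average about 33 days (30-41) of time that must be delivery-free, about 3-5% of unexposed follow-up.
- Comparator preterm incidence under the rule, against entry without the left-edge condition: 10.31% vs 10.52%, ratio 1.020 (index-year weights); 10.44% vs 10.55%, ratio 1.011 (delivery-year weights).
- If 5-10% of pregnancies reaching 27 weeks deliver before 37 weeks, left-edge comparators show 2.5-4.8% preterm against 4.6-8.7% with entry by index date. The ratio for the whole comparator is then 1.028-1.030. Rough check at the low end: 5.6% × (1 − 2.5/4.6) = 2.6% lost.
- Other combinations of these assumptions reach between 3% and 4%. The preterm RR is therefore about 1-4% too high.

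**5. Does a primary decision move?** Adding 3% to the allowed design bias gives 1.25 × 1.03 = 1.2875. Power is then still about 100% at a preterm rate of 4.6%, and about 93% at the 1% floor.

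**6. Feasibility of a tighter rule.** 34,486 + 29,519 = 64,005 unvaccinated pregnancies in 2012-2013; 64,005/15,000 = 4.3 per exposed woman, before the membership and prenatal-care criteria.

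**The case against.** The strongest points on the other side, and what stands of each:

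- **Approximate window, conditional extension.** The documents call the period approximate, and years are added only if matching requires it. True, but approximate edges still leave the index date unconstrained, and the extension has no stated direction.
- **Undefined year in Table 5.** If it means pregnancy-start year, every 2013 conception sits in the 38.3% uptake row, and Table 5 then shows no conflict with the rationale. This stands. That reading also gives one of the larger 2014 shares (20.8%), so the top of the range should not be combined with the 65% uptake figure. Under the index-year or delivery-year readings, where the conflict is direct, the share is about 12-13%.
- **Planned adjustment.** SAP 5.4 acknowledges confounding by indication. SAP 3.2.4 keeps diabetes, Medicaid insurance, health care utilization and (except for preeclampsia) pre-existing hypertension in the primary models. This may reduce right-edge bias in part; calendar year is not among the covariates.
- **Small and conservative left edge.** For non-inferiority this stands. It does not cover the secondary endpoints: SAP 4.3 flags a lower 95% limit above 1, and losing stillbirths from the comparator alone pushes toward such a flag.

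A reader might infer that the 2011 time is free of all events. It is not. Being pregnant on 1/1/2012 shows only that the pregnancy had not ended; preeclampsia or intra-uterine infection before that date can still occur and count. Nor do the documents support the inference that the primary safety conclusion is unreliable: the quantifiable part runs against a false claim of safety, and the rest has no known direction.

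**Conclusion.** The mismatch between admission date and index date is real in the current text of both documents and should be corrected.

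- **2014 edge, the more important one.** About 12-22% of comparators would be indexed in a year from which the protocol's own rationale regards unvaccinated women as selective. The documents do not allow the bias to be sized or signed.
- **2011 edge.** About 4.5-10% would enter conditional on still being pregnant on 1/1/2012. The preterm RR rises by about 1-4%, which is small and conservative against a margin of 2, but in the wrong direction for secondary superiority tests of pregnancy-ending events.

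The shares rest on assumed uniform starts, pregnancy length and even sampling from the pool, and on how Table 5 is read. They are ranges, not findings from the documents. No change in a primary decision is demonstrated.

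**What to change.** In SAP 3.2.1 and protocol 4.1 and 4.4, replace the any-pregnant-day condition with: *assigned index date between 1/1/2012 and 12/31/2013, with the pregnancy ongoing on that date*. Apply the same index-date rule to any added years. Avoid or explicitly flag an extension to 2014 or later, since it conflicts with protocol 3.2; 2011 (60.0% unvaccinated in Table 5) is closer to the rationale than 2014 (34.7%).

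Add the distribution of index year by cohort to table shell 2, and state what Year means in Table 5. If the cohort is already matched, keep it and add a sensitivity analysis of the primary and secondary endpoints restricted to comparators with index dates in 2012-2013.

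The cost is a short wording change and one condition in the matching program. The pool becomes smaller, though with about 4.3 unvaccinated pregnancies per exposed woman before other criteria it should suffice. Some rare strata, such as multiple gestations in small race/ethnicity groups, will be harder to match.
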